#### **Unrelated (clearly not related to the research)**

The occurrence of the AE is not reasonably related in time, OR the AE is considered unlikely to be related to the treatment (biologically implausible).

#### **Probably not related (doubtfully related to the research)**

The administration of the treatment and the AE are not considered reasonably related in time AND the AE could also be explained by causes other than the treatment (concurrent illness/underlying disease, other drugs or procedures).

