### **Relationship to Study Medication**

The Principal Investigator is required to assess whether there is a reasonable possibility that the Study Medication caused or contributed to an AE.

Many terms and scales are used to describe the degree of causality between a Study Medication and an event. The expression “reasonable causal relationship” is meant to convey in general that there are facts (evidence) or arguments to suggest a causal relationship (ICH E2A, III/A/1).

Determination of whether there is a reasonable possibility that a treatment caused or contributed to an AE includes assessing temporal relationships, biologic plausibility, association (or lack of association) with underlying disease, and presence (or absence) of a more likely cause.

As is recommended in FDA draft guidance document, Safety Reporting Requirements for INDs and BA/BE Studies (2010), we define four degrees of relatedness: “unrelated”, “probably not related”, “suspected adverse drug reaction” (SADR) or “adverse reaction”.

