#### **Suspected Adverse Drug Reaction (SADR)**

Suspected adverse reaction means any AE for which there is a reasonable possibility that the treatment caused the AE. A ‘reasonable possibility’ means there is evidence to suggest a causal relationship between the treatment and the AE. A SADR reaction implies a lesser degree of certainty about causality than adverse reaction, which means any AE caused by a treatment.

The Principal Investigator should consider if exposure to the treatment and the AE are reasonably related in time AND the treatment is more likely than other causes to be responsible for the AE or is the most likely cause of the AE.

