### **12.3 Severity (Intensity) of Adverse Events**

The severity of the adverse events should be assessed based on the following grading scale:

- Grade 1 ( Mild): Adverse event that is noticeable to the subject and may require additional therapy;
- Grade 2 (Moderate ): Adverse event that interferes with the subject's activities and requires intervention or additional therapies;
- Grade 3 (Severe): Adverse event that is intolerable, or necessitates additional therapy or places the subject at immediate risk of harm;
- Grade 4: Adverse event that is life-threatening or disabling (hospitalization);
- Grade 5: Adverse event that results in Death.

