### **12.4 Expected and Unexpected Adverse Events**

“Expected” AEs are those that have been previously reported as associated with the disease process. All others are to be recorded as “Unexpected”.

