**13.1 Risk of Losartan Administration**

A full description of expected side effects can be found in Losartan's directions for use <https://www.bioportfolio.com/resources/drug/15151/Losartan-Potassium-Sandoz-Inc.html>

Known side effects include dizziness, headache, diarrhea, stomach pain, muscle cramps, leg or back pain, insomnia, tiredness and cold or flu symptoms such as stuffy nose, sneezing, sore throat, fever and cough. In addition, there is a chance that administration of losartan will not improve the outcomes of microfracture.

Subjects will be fully informed about expected side effects of losartan and will be instructed to inform the Primary Investigator should these symptoms become apparent. Informed consent will include information revealing that it is unknown if losartan will improve the outcomes of microfracture.

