### **14.1 Termination of Enrollment by the Principal Investigator**

The Principal Investigator may terminate study enrollment at any time for any of the following reasons.

1. Any unexpected serious or life-threatening AE that cannot be determined to be unrelated to Study Medication;
2. It is determined that the protocol precipitates multiple subject non-compliance issues beyond reasonably missed follow-up.

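### Three adverse-event rules do not classify as intended: 'probably not related' sits inside 'unrelated', needing therapy alone makes an event grade 3, and 'expected' has conflicting scopes

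*Combined protocol and SAP*

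**What the plan says.** **Relatedness (Section 12.2, Relationship to Study Medication).** The protocol states "we define four degrees of relatedness".

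- *Unrelated*: "The occurrence of the AE is not reasonably related in time, OR the AE is considered unlikely to be related to the treatment", with biological implausibility added in brackets as the meaning of the second branch.
- *Probably not related*: drug and event "are not considered reasonably related in time AND the AE could also be explained by causes other than the treatment".
- *Suspected adverse drug reaction (SADR)*: first defined by a reasonable possibility that the treatment caused the event. A later paragraph asks the investigator to consider whether there is a time link and "the treatment is more likely than other causes to be responsible for the AE", or the treatment is the most likely cause.
- *Adverse reaction*: a subset of suspected reactions, where there is reason to conclude that the drug was the cause.

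**Severity (12.3).** Grade 1 is perceptible to the subject, with additional therapy possible. Grade 2 interferes with activities and also requires intervention or additional therapy. Grade 3 is an "Adverse event that is intolerable, or necessitates additional therapy or places the subject at immediate risk of harm".

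**Expectedness.** Under 12.4, expected events "are those that have been previously reported as associated with the disease process", and everything else is unexpected. Section 13.0 counts both osteoarthritis risks and sequelae of microfracture as expected. Section 13.1 says "Subjects will be fully informed about expected side effects of losartan".

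**Where the categories are used.** The first ground for ending enrolment in 14.1 is "Any unexpected serious or life-threatening AE that cannot be determined to be unrelated to Study Medication". Section 12.6.1 sends serious and unexpected events to the Medical Monitor within 24 hours and, for subjects on losartan, to FDA within 7 days. Section 12.2 promises that all events will be tabulated and summarized. The primary safety endpoint in 9.4 is the occurrence of adverse events.

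**The concern.** A classification scale works if each event lands in one category and two careful assessors, given the same facts, reach the same one. Here the relatedness and severity scales let one event meet two categories, and the expectedness rule gives different answers in different sections. No section says which category or section takes precedence.

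Safety is one of the two primary objectives. The codes are also used during the trial: relatedness and expectedness appear in the 14.1 ground for stopping enrolment, and expectedness appears in the expedited reports of 12.6.1. An event coded one way would be reported, or would count toward stopping; coded the other way, equally in line with the text, it would not.

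**Working it through.** The plan gives no figure to reproduce on this point. The check is logical: each rule is written as a condition and every coherent combination is listed.

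**1. Relatedness.** Let T = related in time, P = plausible, O = another cause could explain the event, M = treatment more likely than other causes. From Section 12.2:

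- Unrelated = not T, or not P (reading the bracketed implausibility as the meaning of the second branch)
- Probably not related = not T, and O
- SADR, comparative standard = T and P and M

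There are 2^4 = 16 combinations. Six are incoherent because M holds without both T and P. One more is incoherent because T and P hold, there is no other cause, and yet the treatment is not the more likely one. That leaves 16 - 6 - 1 = 9.

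| T | P | O | M | Categories met |
|---|---|---|---|---|
| no | no | no | no | unrelated |
| no | no | yes | no | unrelated **and** probably not related |
| no | yes | no | no | unrelated |
| no | yes | yes | no | unrelated **and** probably not related |
| yes | no | no | no | unrelated |
| yes | no | yes | no | unrelated |
| yes | yes | no | yes | SADR |
| yes | yes | yes | no | none under the comparative standard; can be SADR under the reasonable-possibility standard |
| yes | yes | yes | yes | SADR |

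*Probably not related* requires not T, and not T is already enough for *unrelated*. So 2 of the 2 rows that meet it are also *unrelated*, and it never applies alone. The eighth row is where the two SADR standards disagree. *Adverse reaction* is a subset of SADR and adds no row.

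**2. Severity.** Let I = interferes with activities, A = needs additional therapy, V = needs some other intervention, X = intolerable, R = immediate risk of harm.

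- Grade 2 = I and (A or V)
- Grade 3 = X or A or R

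Among the 16 combinations with I, 12 have A or V, and these are grade 2. Of the 12, 8 have A, and all 8 also meet grade 3. The other 4 have V without A, and 3 of them have X or R. So 8 + 3 = 11 of 12 grade 2 combinations also meet grade 3. The exception needs an intervention that does not count as additional therapy. A merely perceptible event that needs a simple remedy fits grade 1 and meets grade 3.

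These are counts of logical combinations, not expected frequencies of events.

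**3. Expectedness.**

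| Type of event, not otherwise reported with the disease process | 12.4 | 13.0 | 13.1 |
|---|---|---|---|
| Sequela of microfracture | unexpected | expected | not addressed |
| Listed losartan side effect, such as dizziness | unexpected | not addressed | called expected |

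The *Adverse Reaction* text in 12.2 refers to a Section 15.1 for events common with the drug. Section 15.0 is Statistical Considerations and has no 15.1, so that pointer does not settle the matter.

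**4. Effect on 14.1 and 12.6.1.**

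- A serious unexpected event with no time link and another possible cause: coded *unrelated*, it does not meet the 14.1 ground; coded *probably not related*, it arguably does. Both codes follow the text.
- A serious known losartan effect not previously reported with the disease: unexpected under 12.4, so it can count under 14.1 and is reportable under 12.6.1 as serious and unexpected; taken as expected under 13.1, it is neither.

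**The case against.** Several stronger readings are tempting, and the documents do not support them.

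- *A time-linked, plausible event with a competing surgical cause has no category.* A reader might infer this from the comparative SADR wording alone. But the definition opens with the reasonable-possibility standard, which can take in that event. What stands is that two standards give different answers. Such an event also plainly has not been determined to be unrelated, so that part of the 14.1 test still works for it.
- *Nearly every event is close in time to both drug and surgery.* Dosing lasts one month, while target-hip events are collected to 18 months, so later hip events may have only a weak time link to the drug.
- *Severity faults distort the stopping rule.* They do not. Serious and life-threatening are defined separately in 12.5, and grades do not enter 14.1.
- *Planned safety results by category are compromised.* No analysis by relatedness, severity or expectedness is specified.
- *The arms would be misclassified differently.* The assessing investigator is blinded, and nothing in the documents points to a difference by arm.

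Two further arguments limit the consequence. First, the literal 12.4 rule makes more events unexpected, which among serious events errs toward reporting; and 13.1 uses the word when describing what subjects are told, not to set a coding rule. That is fair, but 13.0 also uses the word more widely than 12.4, and an assessor has no stated precedence. Second, 14.1 leaves stopping to the investigator's discretion, and 14.2 lets the Medical Monitor stop enrolment on safety signals whatever the codes. That too is fair, although 14.0 says that a triggered rule will stop enrolment, so the force of the criterion is itself stated in two ways.

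**Conclusion.** The point holds for three rules as written. *Probably not related* is never a distinct category (2 of 2 combinations are also *unrelated*), and SADR has two standards. Grade 3 takes in 11 of 12 grade 2 combinations and some grade 1 events. The scope of *expected* in 12.4 conflicts with 13.0 and 13.1.

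The reach is limited. Total adverse-event occurrence does not change. The relatedness overlap and the expectedness conflict bear on 14.1, and the expectedness conflict also on 12.6.1. The severity fault affects only the recorded grades and any summary of them. Because 12.5 confines serious events to death and life-threatening events, few events may reach those rules in 40 subjects; the documents give no event rate, so no number can be put on it.

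The relatedness result assumes that *unlikely* in the *unrelated* definition means biologically implausible, as its bracket says. A broader reading would enlarge *unrelated* and leave the overlap in place. The severity count assumes that some interventions are not additional therapy; if all are, every grade 2 event meets grade 3.

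**What to change.** Change the protocol and case-report-form wording before events are coded.

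1. **Relatedness.** Rewrite the definitions as one ordered scale with a single SADR standard. For example: apply *unrelated* first (no time link, or implausible); give *probably not related* only to events that are not *unrelated* and do not meet the SADR standard; treat all remaining events as SADR or, where there is reason to conclude that the drug was the cause, adverse reaction. Each event then falls in exactly one category. Confine *unlikely* to implausibility, so that *probably not related* is not emptied again.
2. **Severity.** Reword the grades so that needing additional therapy does not by itself meet grade 3.
3. **Expectedness.** Reconcile 12.4 with 13.0 and 13.1 so that one reference list, chosen by the sponsor, defines *expected* for both 12.6.1 and 14.1. Replace the reference to Section 15.1 with a working one. The discretionary wording of 14.1 and the automatic wording of 14.0 should be reconciled at the same time.

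The cost is an amendment with IRB approval and revised form text. No new data, visits or subjects are needed.

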#### **Suspected Adverse Drug Reaction (SADR)**

Suspected adverse reaction means any AE for which there is a reasonable possibility that the treatment caused the AE. A ‘reasonable possibility’ means there is evidence to suggest a causal relationship between the treatment and the AE. A SADR reaction implies a lesser degree of certainty about causality than adverse reaction, which means any AE caused by a treatment.

The Principal Investigator should consider if exposure to the treatment and the AE are reasonably related in time AND the treatment is more likely than other causes to be responsible for the AE or is the most likely cause of the AE.

#### **Adverse Reaction**

An adverse reaction means any adverse event caused by a drug. Adverse reactions are a subset of all suspected adverse reactions for which there is reason to conclude that the treatment caused the event.

If the event is felt by the Principle Investigator to be either a SADR or an adverse reaction, every effort will be made to identify the event as related to the Study Medication. Adverse events that are generally felt to be attributable to the Study Medication occur in close temporal relationship to the onset of dosing. A discussion of AEs that are common with the Study Medication is found in the [Section 15.1](#) of this document

---

All adverse reactions and SADRs will be followed until resolution or the Investigator judges the experience to be chronic or stable.

### **12.3 Severity (Intensity) of Adverse Events**

The severity of the adverse events should be assessed based on the following grading scale:

- Grade 1 ( Mild): Adverse event that is noticeable to the subject and may require additional therapy;
- Grade 2 (Moderate ): Adverse event that interferes with the subject's activities and requires intervention or additional therapies;
- Grade 3 (Severe): Adverse event that is intolerable, or necessitates additional therapy or places the subject at immediate risk of harm;
- Grade 4: Adverse event that is life-threatening or disabling (hospitalization);
- Grade 5: Adverse event that results in Death.

### **12.4 Expected and Unexpected Adverse Events**

“Expected” AEs are those that have been previously reported as associated with the disease process. All others are to be recorded as “Unexpected”.

### **12.5 Serious Adverse Events**

An AE or suspected adverse reaction is considered “serious” if, in the view of either the Principal Investigator, it results in any of the following outcomes:

- Death;
- A life-threatening adverse event.

An AE or suspected adverse reaction is considered “life-threatening” if, (in the view of the Principal Investigator) its occurrence places the patient or subject at immediate risk of death. It does not include an AE or suspected adverse reaction that, had it occurred in a more severe form, might have caused death.

Serious and/or unexpected adverse event(s) may present as either a local or systemic response, or both, which may present as an anaphylactic response associated with generalized urticaria, shortness of breath, or respiratory or circulatory arrest.

Subjects will be instructed to contact the study site immediately if a systemic reaction occurs between scheduled study visits. Subjects may be assessed initially over the phone and may be asked to return to the study site for an additional visit to assess the reaction.

## **12.6 Reporting of Adverse Events**

### **12.6.1 Appointment of a Non-Blinded Medical Monitor and FDA**

An Independent Medical Monitor will be selected to oversee study safety.. This individual is to be an appropriately certified physician experienced in the management of blood pressure.. He/she will be unblinded to Study Medication.

The portion of this study which is greater than minimal risk involves administration of losartan or placebo for 1 month following enrollment in the study. All adverse events will be monitored by the blinded Study Team during this time period.

The Principal Investigator will be responsible for confirming the severity of all adverse events. All serious and unexpected adverse events will be reported to the unblinded Independent Medical Monitor within 24 hours of their disclosure to the Principal Investigator. The Medical Monitor will review data or events reported by the Study Team within 72 hours of disclosure to the Medical Monitor.

During this time appropriate care will be given to the study subject. If managing adverse events requires unblinding to the any member of the Study Team, the appropriate team member will disclose the group identity to the necessary medical provider.

The IRB will be notified of unanticipated and serious adverse events within 5 business days of identification. This reporting may come from the Study Team, the Independent Medical Monitor, or both.

If a subject experiences a serious and unexpected adverse event while taking losartan, FDA will be notified by telephone or facsimile within 7 days, and in writing within 15 days hours (after the Principal Investigator's initial receipt of the information).

Each written notification may be submitted on FDA Form 3500 or in a narrative format and shall bear prominent identification of its contents, i.e., "Med Watch Safety Report".

---

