| Screening Tools:
(At preoperative visit) | 
Standard of Care Data Collected
 
Basic demographic data, medical and surgical history, medication review, age, gender, body mass index and chronicity of the injury, co-morbidities, smoking status, range of motion, strength and size of the cartilage lesion will be recorded. Circumduction evaluation exercises and range of motion restrictions will be evaluated. Patient Reported Outcomes (PRO) tools which will be repeated, at key study intervals will be performed and a T2 MRI of the hip will be performed as standard of care diagnosis.
  |
| Subject Follow-up:                          | 
All adverse events will be assessed during Study Medication administration and for 5 days (+/- 3) days after medication completion. After Study Medication administration only those adverse events related to the target hip will be collected. In addition, the following data will be collected:
 
Visit 1: Post Op Day 1:
 
Subject discharge for the hospital is anticipated to occur on POD1. At discharge the subject will be provided with a blood pressure cuff and be trained on “at home” blood pressure monitoring and recording. They will also be provided with a prescription for Study Medication which will be written in a blinded format for either losartan or placebo. Subjects will be instructed to visit the Vail Hospital Pharmacy to obtain the correct, blinded Study Medication. Study Medication Logs, and Blood Pressure Logs will be provided, with instructions for completion.
 
Subjects will be instructed to undergo post-operative physical therapy, and they will be provided with a document outlining recommended content. They will also be provided with a
 |

|  |   |
|--|---|

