### **12.2 Recording Adverse Events**

Adverse events that occur up to 35 days +/- 3 days after the beginning Study Medication administration will be recorded. Terms should be recorded consistently, using acceptable medical terms. When possible, a diagnosis should be identified as the AE (i.e., disease or syndrome) rather than the component signs and symptoms, and recorded on the case report form (e.g., record congestive heart failure rather than dyspnea, rales and cyanosis). However, signs and symptoms considered unrelated to encountered syndromes or diseases are to be

---

recorded as individual AEs (e.g., if congestive heart failure and severe headaches are observed at the same time, each experience is to be recorded as an individual AE). The AE should not be recorded as a procedure or clinical measurement (i.e., a laboratory or vital sign) but should reflect the reason for the procedure or diagnosis.

Death is considered to be an outcome of an AE. The cause of death (rather than the term “death”) should be recorded on the serious AE and death report case report forms.

Subjects should be encouraged to report AEs spontaneously or in response to general, non-directed questioning. At each required visit (or whenever reported) during the study, all AEs that have occurred since the previous visit must be recorded on the AE case report form.

All AEs, regardless of seriousness, severity, or presumed relationship to the treatment must be recorded using medical terminology

All AEs must be followed until resolution or until a stable clinical endpoint is reached. All measures required for AE management and the ultimate outcome of the AE must be recorded in the study document. All adverse events that occur in the study population will be tabulated and summarized.

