### **14.3 Removal of Subjects from the Study**

Principal Investigators may remove a subject from the study if:

1. Subject demonstrates poor compliance with study protocol;
2. There is concurrent illness or required medical treatment that interferes with study assessments;
3. The Principal Investigator determines that the subject's health, safety or welfare is at risk.

For subjects taking losartan, symptomatic hypotension, significant electrolyte imbalance, acute renal failure, or severe nausea or vomiting precluding medication compliance will result in immediate discontinuation of the subject's course of medication.

---

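### FDA reporting in 12.6.1 is limited to events on losartan, and the Synopsis and 12.2 set different all-event windows for subjects who stop medication early

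*Combined protocol and SAP*

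**What the plan says.** **Reporting (12.6.1).** Three reporting duties stand in one section.

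- Monitor: "All serious and unexpected adverse events will be reported to the unblinded Independent Medical Monitor within 24 hours".
- IRB: "The IRB will be notified of unanticipated and serious adverse events within 5 business days of identification".
- FDA: "If a subject experiences a serious and unexpected adverse event while taking losartan, FDA will be notified". Only this sentence is tied to being on drug, and it names no period after the last dose.

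**Recording.** Three periods are given for all-event capture.

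- Section 12.2 counts from the first dose: "Adverse events that occur up to 35 days +/- 3 days after the beginning Study Medication administration will be recorded".
- The Synopsis counts from the end of medication: "All adverse events will be assessed during Study Medication administration and for 5 days (+/- 3) days after medication completion". Its next sentence reads "After Study Medication administration only those adverse events related to the target hip will be collected", which does not fit the 5-day tail just described.
- Section 12.6.1 refers to the month of administration: "All adverse events will be monitored by the blinded Study Team during this time period".

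**Early stops (14.3).** For subjects taking losartan, a list of events "will result in immediate discontinuation of the subject's course of medication". The section does not say how adverse events are then collected in those subjects.

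**Closing call.** The telephone contact at the expected end of medication records all adverse events. It is at POD 30 in 11.4 and at Day 35 (+/- 3) in the Synopsis and Appendix B. Every later contact records target-hip events only.

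**The concern.** The first issue is regulatory. An event that leads to a stop under 14.3 may be followed by a new, more serious one. If that second event starts after the last dose, the literal FDA rule does not reach it, although the adjoining rules do. Section 12.4 does not remove the gap: it treats as expected only what is already associated with the disease process, so a drug-related event would count as unexpected. The on-drug wording is what excludes it.

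The second issue concerns a primary endpoint, the occurrence of adverse events (9.4). Two windows that agree for completers but part for early stoppers leave the team without one definition of the period over which events are counted. If early stops were commoner on losartan and the Synopsis window were applied from the actual last dose, the losartan arm would have fewer days in which events could be counted.

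**Working it through.** **1. Reproducing the 12.2 figure.** Inputs: dosing for one month (section 6.0), a tail of 5 +/- 3 days (Synopsis), and 35 +/- 3 days from first dose (12.2). The length of the month is an assumption.

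- 30 days: 30 + 5 = 35, range 32 to 38. This matches 12.2 exactly.
- 28 days: 28 + 5 = 33, range 30 to 36.
- 31 days: 31 + 5 = 36, range 33 to 39.

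For completers the two windows are the same rule within a day or two.

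**2. Early stoppers.** Take the last dose on day k and read completion as the actual last dose. The Synopsis window ends at k + 5. The 12.2 window ends at day 35 whatever k is. The gap is 35 - (k + 5) = 30 - k.

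| Last dose (day) | Synopsis end (range) | 12.2 end (range) | Gap (days) | Days after last dose covered by 12.2 |
|---|---|---|---|---|
| 3 | 8 (5 to 11) | 35 (32 to 38) | 27 | 32 |
| 8 | 13 (10 to 16) | 35 (32 to 38) | 22 | 27 |
| 14 | 19 (16 to 22) | 35 (32 to 38) | 16 | 21 |
| 21 | 26 (23 to 29) | 35 (32 to 38) | 9 | 14 |
| 30 | 35 (32 to 38) | 35 (32 to 38) | 0 | 5 |

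For a stop on day 8, capture is 1 - 13/35 = 63% shorter under the Synopsis.

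**3. What this could do by arm (illustration only).** Suppose proportions sL (losartan) and sP (placebo) stop on day 8 and everyone else completes. The difference in mean capture is (sL - sP) x 22 days. The protocol gives neither proportion. With sP = 0:

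- sL = 10%: 35 - 2.2 = 32.8 days, 6% less;
- sL = 20%: 35 - 4.4 = 30.6 days, 13% less;
- sL = 30%: 35 - 6.6 = 28.4 days, 19% less.

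If sL = sP the difference is zero. With 20 subjects per arm, 10% is two people.

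**4. The FDA trigger, by example.** A subject's last dose is on day 8, and a new life-threatening, unexpected event begins on day 9.

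| Rule | Reaches the event? |
|---|---|
| 12.2 recording (to day 35) | Yes |
| Synopsis recording (to about day 13) | Yes |
| Monitor, 24 hours | Yes |
| IRB, 5 business days | Yes, if unanticipated |
| FDA | No, read literally |

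**5. Timing of the closing call.** Dosing begins on POD 2, so 35 +/- 3 days from first dose ends at POD 2 + 35 = 37 (34 to 40). A call at POD 30 is 28 days after first dose, before the window closes. A call at POD 35 (32 to 38) is 33 days after first dose (30 to 36). On the POD 30 timing, no later scheduled contact asks about non-hip events in the rest of the window.

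**The case against.** The strongest reply is that the protocol already covers these subjects. Monitor and IRB reporting have no on-drug limit. Under 12.2, adverse events are followed to resolution or a stable endpoint. Home blood pressure continues weekly to three months (6.0). The closing call is set by calendar time and goes to each subject, and Appendix B marks its adverse-event entry without the target-hip restriction. Completion in the Synopsis may mean the end of the planned course, in which case it is 12.2 in shorthand. On the FDA sentence, the phrase may be meant only to distinguish losartan from placebo. An event that starts on drug and worsens after a stop has its onset on drug under the protocol's definition. Section 16.0 separately binds the investigator to applicable regulations.

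Much of this stands, and it rules out three stronger readings that a reader might infer.

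- *Safety oversight lapses when the tablets stop.* It does not: of the three reporting duties, only the FDA sentence is tied to being on drug.
- *Early stoppers are watched least.* Under 12.2 a subject who stops on day 8 has 27 days of all-event capture after the last dose, against 5 for a completer. The reading needs the last-dose meaning of completion and has to set aside both 12.2 and the fixed call.
- *The adverse-event comparison is biased towards losartan by 6% to 19%.* Those figures need the last-dose reading, assumed stopping rates and no placebo stops. The days lost are also off-drug days. Section 5.3 reports that adverse responses came early with no sign of accumulation, so days lost are not events lost in proportion. The event that caused the stop is itself counted. Although 14.3 is worded for subjects taking losartan, the investigator is blinded, so that wording does not establish an imbalance in stops.

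What the reply does not remove is the text. New-onset events after the last dose are literally outside the FDA rule. Following recorded events to resolution does not capture new ones. The Synopsis and 12.2 use different anchors, and the call meant to bridge them has two dates.

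**Conclusion.** The point holds as a matter of rules that need reconciling and should be corrected. The FDA trigger omits new serious and unexpected events that begin after the last losartan dose. That gap follows from the wording and needs no assumption about rates. It is narrow, because 12.5 limits serious to death or life-threatening events and the losartan arm has 20 subjects.

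The two all-event windows agree at day 35 for a 30-day course. They diverge only for early stoppers, and only if completion means the actual last dose; a stop on day 8 then gives about day 13 against day 35. Uneven capture on a primary endpoint is therefore possible under the Synopsis reading. Its size cannot be fixed from the documents, and the arm-level figures above are illustrations, not estimates.

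**What to change.** 1. In 12.6.1, have the FDA trigger cover serious and unexpected events in subjects assigned to losartan with onset from first dose to the end of the 12.2 window, whether or not medication has been stopped. The unblinded Monitor identifies the arm, so the blinded team need not learn it.
2. In the Synopsis, replace the window tied to medication completion with the fixed 12.2 window from first dose, for all treated subjects in both arms. Start the target-hip-only rule when that window closes.
3. State that subjects who stop early keep the scheduled all-event call at the end of the window. Reconcile its timing across 11.4, the Synopsis and Appendix B, counting from first dose so that the call does not come before the window ends.

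These changes concern reporting and capture only; the 14.3 stop criteria are not altered. The cost is a short amendment and an occasional extra FDA report. The call to early stoppers is already scheduled.
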